
40% less patient-controlled opioid analgesia use than controls during the 48-hour post-operative period, with lower pain ratings^{26, 27, 30}. This series of studies was the first to demonstrate the potential of brain stimulation technology to be part of a standard post-operative pain-management strategy, however TMS is more complicated to deliver than tDCS, has more adverse events, and is more cumbersome in the post-operative setting. In two independent preliminary pilot studies, the PI has shown that tDCS can reduce post-operative PCA use by as much as 46% while simultaneously reducing subjective pain ratings. Thus, a handful of preliminary studies have demonstrated the potential for brain stimulation techniques to adjunctively manage post-operative pain, but a more definitive trial is needed to evaluate the efficacy of tDCS using a more rigorous experimental design. Further more data is needed to determine optimal tDCS dosing parameters before tDCS will become a viable clinical intervention for post-operative pain across surgical specialties.

Aim-1: Determine the effects of transcranial direct current stimulation (tDCS) on post-operative pain, patient-controlled analgesia (PCA) use, and post-surgical complications during the 48-hour post-operative period following total knee arthroplasty (TKA) or total hip arthroplasty (THA).

Hypothesis 1: Real tDCS (over sensory/motor and dorsolateral prefrontal cortices) will be associated with decreased PCA morphine-equivalent usage (primary outcome), decreased pain ratings (secondary outcome), and decreased post-operative complications compared to sham tDCS.

Aim-2: Collect preliminary data regarding dose-dependent effects of tDCS on post-operative pain, PCA morphine-equivalent usage, and 6-month outcomes.

Hypothesis 2a: The analgesic benefits of tDCS will be dose dependent such that one 20-minute post-operative tDCS session will be superior to sham, two sessions will be superior to one session, and four sessions will produce the largest analgesic effects in the present study.

Hypothesis 2b: Patients receiving higher doses of real tDCS will evidence lower incidence (and dose) of 6-month opioid medication use, reduced pain, and better quality of life.

B. BACKGROUND AND SIGNIFICANCE

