Statistical Analysis and Power: The orthopaedic surgeons at the Ralph H. Johnson VAMC conduct ~100 unilateral total knee arthroplasties and ~50 unilateral total hip arthroplasties each year . Thus, in order to meet the proposed n-size of the current study, 24 (out of 100) participants will need to be eligible and interested in participating in the trial each year. We will over recruit to permit for drop-outs and participants lost to follow-up. For analysis of primary outcomes associated with Aim-1, participants receiving any active tDCS (groups 1,2 & 3) will be collapsed and compared to the sham-only group. Multivariate multiple regression will be used with group-assignment entered into the model as a binary predictor. Surgery and anesthesia duration, depression & anxiety scores, sex, age, pre-tDCS pain, (ROM) Means and pre-op chronic opioid status will be entered into the model as covariates to permit for statistical control of these potentially confounding variables. Overall differences between real and

sham tDCS groups will then be examined for our primary outcomes: total post-op PCA morphine-equivalent dose, VAS pain-on-average ratings, and mean number of post-operative complications. Using the most conservative effect-size estimate from our series of pilot studies ($d=.70$), with 90 patients in the active tDCS group and 30 in the active-sham group, power is good to detect significant effects if they exist ($\alpha=.016$ (corrected for multiple DV's); $1-\beta >.80$; see figure 9). For Aim-2, MANCOVA will be conducted using all 4 groups and all primary dependent measures in the same model (controlling for surgery and anesthesia duration, depression & anxiety scores, pre-tDCS pain, physical rehab measures and chronic opioid status). With four groups of 30 patients each, assuming a moderate effect size $f^2(V)=.2$, and alpha of .05, power is good detect significant main effects in the model ($1-\beta >.80$). Secondary analyses will be conducted to evaluate long-term effects of tDCS on pain, functioning and quality of life (i.e., 2-wk, 4-wk, 8-wk, 3-month and 6 month-follow-up).

Problems/Challenges/Potential Pitfalls: The proposed tDCS device is an FDA-approved iontophoresis device, and its use for tDCS applications is off-label. The tDCS procedure is minimal-risk and FDA-

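### If Aim-1 keeps three primary outcomes, Holm's step-down test would give the same error control as the implied .016 split, with equal or greater power

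*Combined protocol and SAP*

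**What the plan says.** The Statistical Analysis and Power section (part D) pools the three groups with any active stimulation: "participants receiving any active tDCS (groups 1,2 & 3) will be collapsed and compared to the sham-only group". The model is a multivariate multiple regression with covariates. The section lists as "primary outcomes: total post-op PCA morphine-equivalent dose, VAS pain-on-average ratings, and mean number of post-operative complications". Its power sentence takes d=.70, "with 90 patients in the active tDCS group and 30 in the active-sham group", and an alpha of .016, described as "corrected for multiple DV's", and states power above .80.

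The section gives no rejection rule apart from that sentence. No step-down procedure, testing order or simultaneous confidence intervals appear anywhere in the document. The overall .05 is not written for Aim-1; it is inferred from .05/3.

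Hypothesis 1 under Aim-1 ranks the outcomes differently: "decreased PCA morphine-equivalent usage (primary outcome), decreased pain ratings (secondary outcome". It gives complications no rank.

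**The concern.** An equal split of alpha holds each outcome to the strictest threshold even after another outcome has been won. Holm's procedure relaxes the threshold after each rejection and still controls the familywise error at .05 under any correlation between outcomes. The usual return for a single-step rule is simple simultaneous intervals, and this plan specifies none. On the three-outcome reading, then, the trial would give up some power on its second and third outcomes without using what the simpler rule offers. This matters most for pain, because the rationale is that stimulation lowers opioid use and pain together.

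**Working it through.** **Inputs from the plan:** d=.70; 90 active and 30 sham; per-outcome alpha .016; three outcomes.

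**Assumptions:** two-sided tests (sidedness is not stated); all 120 patients analysed (no drop-out rate is given); between-outcome correlation 0, .3 or .5 (not given); normal test statistics without covariate adjustment, with complications treated on the same d scale.

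**Step 1: the alpha.** .05/3 = .0167, so .016 is that value rounded down. 3 x .016 = .048, which leaves .002 unused.

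**Step 2: the plan's own power.** Noncentrality = d x sqrt(90 x 30/120) = .70 x sqrt(22.5) = 3.320. The two-sided critical value at .016 is 2.409. Power = Phi(3.320 - 2.409) = Phi(.911) = .82 (.81 with the noncentral t, 118 df). The stated figure of above .80 reproduces.

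**Step 3: Holm.** The smallest p-value is tested at .05/3 = .0167, the next at .05/2 = .025 and the last at .05, stopping at the first failure. Every threshold is at least .016, so whatever the fixed rule rejects, Holm rejects. This held in every one of 400,000 simulated trials per scenario.

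**Step 4: size of the gain.** Entries separated by slashes are for correlation 0 / .3 / .5.

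| True effects | Power for | Fixed .016 | Holm |
|---|---|---|---|
| PCA and pain d=.70, complications 0 | PCA use | .82 | about .85 |
| same | PCA use and pain both | .67 / .70 / .71 | .74 / .76 / .77 |
| all three d=.70 | each outcome | .82 | .90 / .89 / .88 |
| same | all three | .55 / .60 / .64 | .75 / .78 / .80 |
| PCA only d=.70 | PCA use | .819 | .824 |

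Hand check of the second row at correlation 0:

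- Fixed rule: .82 x .82 = .67.
- Holm: power is .823 at .0167 and .860 at .025. Both are rejected if both p-values are at most .025 and at least one is at most .0167: .860^2 - (.860 - .823)^2 = .738. The cases where complications is also rejected add the small remainder, to .74.

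**Step 5: error rate and limits.** With no true effects, Holm's familywise error was .044 to .049 over these correlations. The chance of at least one rejection barely moves (.958 against .959 with all three effects at correlation .5), because Holm's first step is also .05/3. At d=.38, the figure from the single-session ERCP pilot, on all three outcomes, power per outcome is .27 with the fixed rule and .31 to .33 with Holm.

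**The case against.** The strongest reply is that nothing here is wrong. A Bonferroni split is valid, and the plan meets the power it states. That stands: this is an efficiency point.

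Three stronger readings are tempting, and the documents do not support them.

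- A reader might infer that the plan commits to testing each outcome at a fixed .016. The figure occurs only in the power sentence. A per-outcome threshold is the natural reading, but the plan does not state it as a decision rule.
- A reader might infer that the plan misses its own target, because power for PCA use and pain together is .67-.71. The stated .80 is per outcome, and the plan claims no joint power. Holm's .74-.77 would not reach .80 either. If success were defined as winning on both, each test could run at .05 with no split, but the plan does not define success that way.
- A reader might take the all-three gains as what to expect. They need d=.70 on complications, for which no pilot effect size is given.

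The objection with most force concerns the ranking in Hypothesis 1. If PCA use is the sole primary outcome, its power at two-sided .05 is .91. Testing PCA use and then pain in fixed order at .05 would give about .91 x .91 = .83 for both if independent, against .74 for Holm. Adopting Holm without settling the ranking would fix in place a family that Hypothesis 1 contradicts. This stands, and it decides the order of the fix.

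**Conclusion.** The point holds as a conditional, nearly free improvement. If the three-outcome family is kept, Holm at familywise .05 can only add rejections to those of the implied .016 split. That dominance does not depend on the assumed effects or correlations.

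The size of the gain does. It is about 3 points for PCA use, and about 6 to 7 points for PCA use and pain together, when those two effects are d=.70 and complications have none. It is under 1 point when only one effect is real, and 6-8 points per outcome only when all three are d=.70. Correlations of 0 to .5, two-sided tests and full analysis of 120 patients are assumptions. The point lapses if PCA use is the sole primary outcome.

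**What to change.** 1. Reconcile Hypothesis 1 (PCA use primary, pain secondary) with the Statistical Analysis and Power section (three primary outcomes).
2. If the three outcomes are kept, add one sentence: the Aim-1 outcomes are tested by Holm's procedure at familywise .05, with thresholds .0167, .025 and .05 from the smallest p-value up. Describe .016 as the conservative planning alpha only, so that the sample-size statement is unchanged.
3. If PCA use is the sole primary outcome, say so and drop the split for it.

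The cost is one or two sentences, to be written before unblinding. No patients, visits or data are added. The only loss is that simultaneous confidence intervals, should the sponsor later want them, are less simple under Holm.

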tDCS Electrode

Placement: All participants will have an EEG 10-20 cap placed F3 will be marked with a non-toxic felt-tipped pen. The tDCS anode will be placed over the mark (see figure 8) and the cathode will be placed over the right dorsolateral prefrontal cortex (F4). Electrodes will be held in place with Velcro straps.

tDCS Methods: tDCS will be delivered in four 20-minute-sessions (100 minutes total)

[figure not shown]
and will be conducted with the Phoresor-II Auto (Model PM850, Iomed, Salt Lake City Utah, USA) using 2mA current. This constant current device ramps up to the desired amplitude to minimize discomfort for participants and ramps the amplitude back to 0mA at the end of the programmed treatment duration. Electrodes will be standard small (4cm X 4cm) sponge electrodes soaked in a sterile solution of 0.9% sodium chloride insulated by a latex casing. The current density and total charge delivered by the above parameters is consistent with those used safely in the current research literature on tDCS. A very low dose (0.125mL) of topical benzocaine (6%) cream may be applied to the skin beneath the sponge electrodes for ~10 minutes and then removed if the participant experiences strong cutaneous sensations (patient report) during stimulation. After stimulation, a vitamin-E/Aloe cream will be applied to the skin under the electrodes following each treatment to reduce risks associated with skin drying.

tDCS Dosing: Custom-developed software will be used to generate random number sequences and save them in a file-format readable by the tDCS blinding software. Participants will be randomized to one of four groups in order to assess the effects of total tDCS charge on post-operative pain.

Group1 will receive a total of four 20-minute sessions of active 2mA tDCS (2 sessions on post-op day 0; and 2 sessions on post-op day 1)

Group2: will receive a total of two 20-minute sessions of active 2mA tDCS (2 sessions on post-op day 0; and 0 sessions on post-op day1) followed by 2 sessions of sham tDCS (both on post-op day 1).

Figure 8. Trajectory of anodal stimulation associated with the proposed tDCS electrode placement strategy

Group3: will receive a only one 20-minute session of active tDCS on post-op day 0, followed by three sessions of sham tDCS (1 on post-op day 0 and 3 on post-op day 1).

Group4: will receive a total of four 20-minute sessions of sham tDCS (2 sessions on post-op day 0; and 2 sessions on post-op day 1)

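### Aim-2 states an ordered dose hypothesis, but its only test is an unordered four-group MANCOVA; no dose contrast and no one-session-versus-sham comparison is prespecified

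*Combined protocol and SAP*

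**What the plan says.** Aim-2 is framed modestly: "Collect preliminary data regarding dose-dependent effects of tDCS on post-operative pain". Hypothesis 2a is nevertheless directional and ordered: "one 20-minute post-operative tDCS session will be superior to sham, two sessions will be superior to one session, and four sessions will produce" the largest effect. The tDCS Dosing text in section D says the arms will show whether more stimulation beats less. The Competing Trials paragraph gives dose, together with the veteran population, as what sets this study apart from the investigator's other trial.

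Under Statistical Analysis and Power, the Aim-2 analysis is: "For Aim-2, MANCOVA will be conducted using all 4 groups and all primary dependent measures in the same model". The three measures are PCA morphine-equivalent dose, VAS average pain and number of complications. The power statement is for that model's group effect: "assuming a moderate effect size $f^2(V)=.2$, and alpha of .05, power is good detect significant main effects in the model", at 30 per arm, with power above .80.

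For Aim-1, "participants receiving any active tDCS (groups 1,2 & 3) will be collapsed and compared to the sham-only group". No dose score, trend test, planned contrast, pairwise comparison or follow-up procedure appears anywhere. The long-term secondary analyses name no method.

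**The concern.** A four-group MANCOVA asks whether the mean vectors differ in any way. It is as ready to reject when all active arms are equal, or when the gradient runs backwards, as when benefit rises with dose. The hypothesis concerns order and the test does not.

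The first step of Hypothesis 2a, one session better than sham, has no test of its own. Aim-1's pooled comparison can be carried by the two- and four-session arms.

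The four arms will produce usable dose-group means, but the plan does not say which comparison of them answers the dose question. That choice would then be made after seeing four means on each of three outcomes, and a significant MANCOVA could be taken as dose dependence when one session does as well as four.

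**Working it through.** **Inputs from the documents.** 4 arms of 30, N = 120; 3 outcomes; f²(V) = .2; Aim-2 alpha .05; Aim-1 alpha .016, 90 versus 30, d = .70 (Statistical Analysis and Power). Section C pilots: d = .38 (single session, ERCP) and d = 1.0 (four sessions, TKA). **Assumed:** effect patterns across arms, SD 1, outcome correlations 0 to .5, no dropout, and no covariates unless stated.

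**1. The plan's own figure.** Pillai trace: s = 3, df1 = 3 × 3 = 9, df2 = 3 × (120 − 4 − 3 + 3) = 348. The smallest noncentrality convention, N·f² = 120 × .2 = 24, gives power .948. The conventions df2·f² = 69.6 and N·s·f² = 72 give above .999. The claim of more than .80 is correct for the omnibus test.

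**2. The same test with no dose gradient.** Simulated rejection rates at outcome correlation 0 / .3 / .5:

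| True effect at 1, 2, 4 sessions | PCA dose only affected | All three affected |
|---|---|---|
| .70, .70, .70 | .57 / .65 / .79 | .99 / .89 / .79 |
| .38, .38, .38 | .17 / .19 / .25 | .51 / .31 / .25 |

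Repeat runs differ by about .01, so the d = .70 range is about 56-99%. Under the full null the rate is about .05. A reversed gradient (1.0, .7, .4 at correlation .3) is rejected in 85% and 98% of trials. These rejections are correct as group differences but say nothing about increasing dose.

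**3. One session versus sham through Aim-1.** With all active arms at .70, the pooled test at alpha .016 has power .81, matching the plan. With one session inert (0, .70, 1.0), the pooled effect is (0 + .70 + 1.0)/3 = .57 and the test still rejects in about 53-54% of trials.

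**4. A contrast that does address dose.** Sessions 1, 2, 4 have mean 7/3, so the weights are −4/3, −1/3, 5/3, with sum of squares (16 + 1 + 25)/9 = 4.667. Slope = Σ(weight × effect)/4.667. With the error term from all four arms (116 df), SE = 1/√(30 × 4.667) = .0845 SD per session. Two-sided alpha .05, noncentral t:

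| Effects at 1, 2, 4 sessions | Slope | Slope/SE | Power |
|---|---|---|---|
| .25, .5, 1.0 (linear to 1.0) | .250 | 2.96 | .83 |
| .3, .3, 1.0 (two equal to one) | .250 | 2.96 | .83 |
| .38, .70, 1.0 (illustrative) | .199 | 2.35 | .64 |
| .175, .35, .70 (linear to .70) | .175 | 2.07 | .54 |
| .3, .6, .6 (plateau) | .086 | 1.01 | .17 |
| .70, .70, .70 | 0 | 0 | .05 |

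CI half-width is 1.981 × .0845 = .167 SD per session, or .50 SD for four versus one. A linear 0/1/2/4 contrast that includes sham would not serve: with all active arms at .70 it rejects in about 61% of trials.

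**5. One session versus sham directly.** SE = √(2/30) = .258. At d = .38, .38/.258 = 1.47 and power is .31. At d = .70, 2.71 and .77. CI half-width is 1.981 × .258 = .51 SD.

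**6. Effect of covariates.** If covariates explain a share R² of outcome variance, slope/SE is divided by √(1 − R²). The .64 scenario becomes .80 at R² = .3 and .91 at R² = .5. The documents give no R².

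**7. Timing.** Under tDCS Dosing, Group 1 receives "four 20-minute sessions of active 2mA tDCS (2 sessions on post-op day 0; and 2 sessions on post-op day 1", whereas Group 2's two active sessions are "followed by 2 sessions of sham tDCS (both on post-op day 1". Group 3's single active session is on day 0. Active stimulation on day 1 therefore occurs only in Group 1.

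**The case against.** Aim-2 is labelled preliminary and the study is called a pilot. The direction of effect is fixed in advance, and the MANCOVA model will yield four adjusted means that can be inspected. This limits the stakes and is why the remedy should be reported as estimation. It does not supply the missing comparison.

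Four stronger readings are tempting, and the documents do not support them.

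- A reader might infer that the Aim-2 power claim is wrong. It is not; step 1 reproduces it for the test it describes.
- A reader might infer that the plan intends to report a significant MANCOVA as dose dependence. It never says so; the risk comes from its silence.
- A reader might infer that f²(V) = .2 is optimistic. With non-negative correlations, no covariates and the .70 or .38/.70/1.0 patterns it looks high (about .03 to .11). At a correlation of −.3 with all three outcomes affected, the .38/.70/1.0 pattern gives .204, and covariates would also raise it. The documents give no correlations, so one can say only that .2 is not derived.
- A reader might take .38 and 1.0 as pilot evidence of a dose curve. The two pilots differ in procedure, electrode montage and follow-up length, this trial's montage differs from both, and the middle value .70 is assumed.

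It is also fair that the proposed contrasts answer only part of Hypothesis 2a and have limited power. That is a reason to state their precision, not to leave the question without an analysis.

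**Conclusion.** The concern holds. The stated Aim-2 test cannot answer the stated Aim-2 hypothesis. With equal active arms at d = .70 it rejects in about 56-99% of trials, and no other analysis in the plan tests a dose trend or one session against sham. Aim-1 does not fill the gap, since its pooled test rejects in about 53% of trials under an assumed pattern in which one session does nothing.

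That the test has no ordering in it rests on the text alone. The percentages rest on assumed effect patterns and outcome correlations and exclude covariates. This should be corrected, but the preliminary status of Aim-2 keeps it from threatening the trial's main comparison.

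**What to change.** In Statistical Analysis and Power, keep the MANCOVA as the overall test and state that it is not read as evidence of dose dependence. For PCA morphine-equivalent dose, prespecify:

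- (a) a one-degree-of-freedom linear contrast in number of active sessions over the 1-, 2- and 4-session arms, with the error term from all four arms;
- (b) one session versus sham.

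Adjust both for the planned covariates measured before treatment, and say explicitly that the post-treatment physical rehabilitation measures in the Aim-2 covariate list are left out of these contrasts. Report the slope, the one-versus-sham difference and all four adjusted means with 95% CIs, as estimates.

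State the limits. Contrast (a) tests a trend and not the two-versus-one step, is weak under a plateau, and cannot separate number of sessions from day of stimulation.

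Give power only as labelled scenarios without covariate adjustment: for (a), .83, .64 (marked illustrative), .54 and .17 as tabulated; for (b), .31 at d = .38 and .77 at d = .70. Add that adjusted power would be higher by an amount the documents cannot fix. If f²(V) = .2 stays, say where it comes from.

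The cost is wording and two contrasts on data already collected. The drawback is that the power stated for the dose question falls below .80 in most unadjusted scenarios, and dose results for pain and 6-month outcomes remain descriptive.

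### Aim-1's joint three-outcome model, with no missing-data rule, ties PCA dose to the completeness of every other outcome and covariate; separate models with filled-in baseline covariates protect a power margin of about two patients

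*Combined protocol and SAP*

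**What the plan says.** The analysis is set out in section D under Statistical Analysis and Power. For Aim 1 the three active groups are pooled against sham, and "Multivariate multiple regression will be used with group-assignment entered into the model as a binary predictor". The outcomes, all called primary there, are "total post-op PCA morphine-equivalent dose, VAS pain-on-average ratings, and mean number of post-operative complications". (Hypothesis 1 names PCA use as the primary outcome and pain ratings as secondary.) The covariate list opens with "Surgery and anesthesia duration, depression & anxiety scores, sex, age, pre-tDCS pain" and adds range-of-motion (ROM) means and pre-operative chronic opioid status; these "will be entered into the model as covariates to permit for statistical control of these potentially confounding variables". Counting surgery and anaesthesia duration separately, that is nine.

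Power for Aim 1 is stated as above .80 at d = .70 and alpha .016, an alpha already corrected for several outcomes, "with 90 patients in the active tDCS group and 30 in the active-sham group".

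For Aim 2, "MANCOVA will be conducted using all 4 groups and all primary dependent measures in the same model", with seven covariates (no sex or age), at alpha .05.

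The section gives no imputation method, no questionnaire scoring rule for blank items and no analysis set. It promises over-recruitment for drop-outs and loss to follow-up without a number. Planned enrolment elsewhere is 120.

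**The concern.** A standard multivariate regression needs a complete row: every outcome and every covariate. A patient whose pump record is intact but who has no pain-on-average value, depression score, anxiety score or pre-tDCS pain rating then leaves the PCA analysis as well. PCA dose is downloaded from the pump and ought to be the best-recorded outcome, yet its analysis would depend on self-report forms and on a rating taken in the PACU soon after waking.

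Such a cost might be worth paying if the joint fit sharpened the Aim-1 tests. It does not, because every outcome has the same predictors and is judged at its own alpha. What is at stake is power on PCA dose in a design with very little to spare.

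**Working it through.** **1. The plan's figure.** Inputs from Statistical Analysis and Power: 90 active, 30 sham, d = .70, alpha .016. Sidedness is not stated; two-sided is assumed.

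Noncentrality = d × √(n₁n₀/(n₁+n₀)) = .70 × √(90 × 30/120) = .70 × √22.5 = 3.32. The critical t on 118 df is 2.444, which gives power **.808** (.807 with nine df spent on covariates; .819 by the normal approximation). The stated figure reproduces.

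**2. Slack.** Holding the 3:1 ratio, noncentral-t power is .800 at 118 complete cases and .796 at 117. By the normal approximation it is .800 at 115 and .796 at 114. The margin is therefore two patients by t, or five by z.

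**3. What the joint fit gives.** With a common design matrix X, the multivariate estimate is (X′X)⁻¹X′Y. Its column for PCA dose is (X′X)⁻¹X′y for PCA dose alone, which is the separate regression. A numerical check with 120 patients, nine covariates and three correlated outcomes found a largest coefficient difference of about 10⁻¹⁶.

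**4. Cost of incomplete rows.** The documents give no missing-data rate. Assume a fraction m missing independently and completely at random on each of six variables: the three outcomes, BDI, BAI and pre-tDCS pain. The other covariates are taken as complete, and ROM is left out. The number analysed for PCA dose is 120 × (1−m)^k, where k counts the variables that can remove a patient:

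- joint model: k = 6
- separate PCA model, same covariates: k = 4
- separate PCA model, baseline covariates filled in: k = 1

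| m | Joint: N, power | Separate: N, power | Separate + filling: N, power |
|---|---|---|---|
| 2% | 106.3, .749 | 110.7, .770 | 117.6, .799 |
| 3% | 100.0, .718 | 106.2, .749 | 116.4, .794 |
| 5% | 88.2, .652 | 97.7, .706 | 114.0, .784 |

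**5. Splitting the loss.** Joint to separate recovers about 2, 3 and 5 points. Filling the covariates recovers a further 3, 4.5 and 8 (.799 − .770, .794 − .749, .784 − .706). Filling covariates while keeping the joint fit (k = 3) gives .779, .764 and .733. If complications are never missing, the joint model has k = 5 and power .760, .734 and .679, so the joint fit costs only about 1, 1.5 and 3 points.

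**6. ROM.** Table 1 places ROM at 2, 4 and 8 weeks; Procedures and Flow ties it to physical therapy sessions. Either way it follows randomised treatment. It is defined as knee flexion, yet hip patients are enrolled and no hip measure is described. If ROM were missing in 20% and all else complete, N = 120 × .80 = 96 and power is .697 in the joint and the separate model alike, against .808 with ROM left out.

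**The case against.** Four points deserve weight.

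- **The joint model is not the main culprit.** A reader might blame the whole drop on it. Separate regressions with the same covariates lose the same patients for a missing BDI, BAI or pre-tDCS pain score, as step 5 shows. This stands.
- **Deletion is not written down.** A reader might infer that the plan drops anyone with one blank item. No section says so: it is the default behaviour of the named method, and blank items could be prorated. Pain is rated twice daily and around each tDCS session, so one missed rating need not remove a patient if pain on average is summarised over several. Complications come from routine-care tracking and should be nearly complete. These points stand and shrink the joint-fit cost. That sedated or very unwell patients would be lost selectively is possible, but the documents do not show it.
- **Over-recruitment is promised.** Enrolment is therefore not simply fixed at the powered number. But no figure is given, and planned enrolment is still 120. Keeping 120 complete rows in the six-variable joint model needs 120/.8858 = 136, 120/.8330 = 145 or 120/.7351 = 164 patients at 2%, 3% or 5%. The separate model with filling needs 120/.98 = 123, 120/.97 = 124 or 120/.95 = 127.
- **A multivariate test can be useful.** A reader might extend the lack of gain to Aim 2. That would be wrong: the MANCOVA is an omnibus test at .05 that limits multiplicity across outcomes and can use their correlation. On the plan's own inputs its power exceeds .999, and no material Aim-2 loss has been shown.

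**Conclusion.** The point holds for Aim 1. The plan names a joint complete-row method, gives no missing-data rule, and gains nothing from the joint fit for tests made one outcome at a time. On the assumed 2% to 5% missing per variable, power on PCA dose falls from .81 to between .75 and .65. Separate models with filled baseline covariates hold it at .80 to .78. Of the recoverable 5 to 13 points, the joint fit accounts for about 2 to 5, and less if complications are complete; incomplete covariates account for the rest.

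These sizes rest on assumed, independent missingness, complete-case fitting, a two-sided test and the plan's d = .70, with no credit for precision gained from the covariates. A one-sided test would start from .874 and leave more room. The documents do not support reading this as a stated deletion rule, as a loss due wholly to the joint model, or as a defect in the Aim-2 MANCOVA.

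**What to change.** - For Aim 1, fit one covariate-adjusted regression per primary outcome, each at the planned .016, on all randomised patients with that outcome.
- State a scoring rule for partly blank BDI and BAI forms. Fill missing pre-treatment covariates (BDI, BAI, pre-tDCS pain, chronic opioid status) with the overall mean or mode, ignoring group. This is sound because these values precede treatment.
- Do not fill ROM this way. Remove it from the Aim-1 covariates: it is measured after randomisation and is undefined for hip patients, and separate models that keep it still lose those patients.
- Keep the Aim-2 MANCOVA as the omnibus test, and say how missing data are handled there.
- Put a number on the over-recruitment.

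The cost is analysis-plan wording, with no new data collection. Sample sizes may differ slightly between the three outcomes and should be reported with each result.

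### The Aim-2 dose model leaves out sex and age, which the Aim-1 model adjusts for on the same outcomes; adding them is a cheap, probably small, gain in precision

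*Combined protocol and SAP*

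**What the plan says.** Both covariate lists stand in one paragraph of the combined protocol and SAP (section D, Statistical Analysis and Power).

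- **Aim 1** (any active tDCS against sham) lists "Surgery and anesthesia duration, depression & anxiety scores, sex, age, pre-tDCS pain, (ROM) Means and pre-op chronic opioid status". The stated purpose is "to permit for statistical control of these potentially confounding variables".
- **Aim 2** (dose): "MANCOVA will be conducted using all 4 groups and all primary dependent measures in the same model", then "controlling for surgery and anesthesia duration, depression & anxiety scores, pre-tDCS pain, physical rehab measures and chronic opioid status". Sex and age are absent, no reason is given, and no other section restores them.
- **Outcomes:** the primary measures, which Aim 2 reuses, are "total post-op PCA morphine-equivalent dose, VAS pain-on-average ratings, and mean number of post-operative complications".
- **Aim-2 sizing:** "With four groups of 30 patients each", "assuming a moderate effect size $f^2(V)=.2$, and alpha of .05", with power stated to exceed .80.

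Hypothesis 2a orders the doses: one session better than sham, two better than one, four best. No power is given for those comparisons.

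**The concern.** The two models use the same patients and outcomes, yet one treats sex and age as needing control and the other ignores them. Both are known before randomisation and cannot be altered by treatment. Both will vary: eligibility runs from 25 to 90 years, and the enrolment table plans 70 women and 50 men. The background section itself links older age to post-operative cognitive problems and opioid side-effects, and complications are one of the three outcomes.

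The omission falls where the groups are smallest. The tDCS Dosing section describes random number sequences and mentions no stratification by age or sex, so chance imbalance between arms of 30 is left to the model. At stake are some precision in the dose comparisons and a consistent, pre-specified treatment of two baseline variables.

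**Working it through.** **1. The plan's own Aim-2 figure.** Four groups, three outcomes, N = 120, f²(V) = .2, alpha .05. For Pillai's V, s = min(3, 3) = 3.
- df1 = 3 × 3 = 9. With no covariates, df2 = 3 × (116 − 3 + 3) = 348.
- Noncentrality = f² × s × N = .2 × 3 × 120 = 72.
- Power is above 99.9%. It stays above 99.9% with 8 covariate df (df2 = 324) or 10 (df2 = 318), and with the alternative noncentrality f² × df2.

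The stated power above .80 is therefore true and does not depend on sex and age.

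**2. Chance imbalance.** The SD of a chance difference in mean age, in units of the age SD, is:
- 30 vs 30: √(1/30 + 1/30) = 0.26
- 90 vs 30: √(1/90 + 1/30) = 0.21

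It is about 22% larger between two dose arms than in the Aim-1 comparison.

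**3. Effect of adding sex and age on a 30 vs 30 comparison.** Inputs:
- Existing Aim-2 covariates counted as 8 df: surgery duration, anesthesia duration, depression, anxiety, pre-tDCS pain, chronic opioid status, and rehabilitation measures taken as 2 (an assumption).
- Error df = 120 − 4 − 8 = 108, falling to 106 after the addition.
- Variance factor for estimating k covariates: 1 + k/(N − g − k − 1), which is 1 + 8/107 before and 1 + 10/105 after.
- R² is the share of residual variance that sex and age explain beyond the other covariates. The documents give no value, so a range is shown.
- d = .70 is borrowed from the Aim-1 power statement and taken in units of the residual SD after the existing covariates. Alpha is .05, two-sided.

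SE ratio (after/before) = √[(1 − R²) × (1 + 10/105)/(1 + 8/107)] = √[(1 − R²) × 1.0190].

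Break-even R² = 1 − 1/1.0190 = .019.

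Power comes from the noncentral t. Before the addition, the noncentrality is .70 × √15 / √(1 + 8/107) = 2.615 on 108 df, giving 73.6%. After it, the noncentrality is .70 × √15 / √[(1 − R²)(1 + 10/105)] on 106 df.

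| Assumed R² | SE ratio | Power, d = .70 (73.6% without) | Power, d = .50 (45.7% without) |
|---|---|---|---|
| 0 | 1.010 | 72.8% | 45.0% |
| .02 | 0.999 | 73.7% | 45.7% |
| .05 | 0.984 | 75.0% | 46.9% |
| .10 | 0.958 | 77.2% | 48.9% |
| .20 | 0.903 | 81.9% | 53.6% |

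**4. Equivalent patients**, 120/ratio² − 120:
- R² = .05: 120/.9839² − 120 = 4.0
- R² = .10: 120/.9577² − 120 = 10.8

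**The case against.** The best case against is that little hangs on this. The documents give no evidence of how strongly sex or age predicts these outcomes, and below an R² of about .02 the addition is a slight loss. The only test specified for Aim 2 is the four-group MANCOVA, whose power at the stated effect size is above 99.9% either way. The 30 vs 30 contrast is not itself a named analysis, d = .70 comes from Aim 1, and Aim 2 is described as gathering preliminary data. All of that stands, and it keeps the point small. It does not remove it: Hypothesis 2a can only be examined by comparing individual arms, and the plan's own rationale for Aim 1 treats both variables as needing control.

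A reader might infer more than the documents support:

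- **Bias.** Under randomisation, imbalance in sex or age is chance. Omitting them costs at most efficiency and consistency.
- **Free precision.** Using √(1 − R²) alone, with 116 error df, gives SE factors of .975 and .949 for R² of .05 and .10, 6-13 extra patients, and power rising from 76.7% to 78.8-80.9%. That charges nothing for the covariates already planned or for the two added. Once they are charged, power passes 80% only at R² near .20.
- **Conflicting estimates.** Aim 2 as written gives a four-group test, not a second pooled active-against-sham estimate, so no two planned estimates are shown to disagree.

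**Conclusion.** The inconsistency is real and unexplained, and correcting it is a worthwhile minor improvement. The downside is capped at about a 1% larger standard error and less than one point of power. For R² of .05 to .10 the standard error falls 1.6-4.2%, equal to about 4-11 patients, and power at d = .70 rises by 1.4 to 3.6 points.

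These figures rest on an assumed R², about 8 covariate df already in the model, linear outcomes with constant variance, a two-sided alpha of .05, and no dropout. The gain would appear in the dose comparisons, not in the omnibus test as powered. The other gain is that both aims would handle sex and age in the same pre-specified way.

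**What to change.** Before unblinding, add sex and age to the Aim-2 covariate list, coded as in Aim 1, or state why they are left out. The cost is one line of text and two error degrees of freedom; both variables are already needed for Aim 1, so no new data, visits or patients are required.

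The change concerns sex and age only. Both lists also carry rehabilitation or range-of-motion measures, under different wording. Table 1 schedules range of motion at 2, 4 and 8 weeks, and Procedures and Flow collects it around physical therapy sessions. These are post-operative values; this fix neither endorses them as covariates nor reconciles their wording.
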